	
having a $\geq 50\%$ reduction compared to baseline in the mean number of stress incontinence episodes per day as assessed by the 3-day voiding diary
 
 • Change in the number of stress incontinence episodes per day as measured by the 3-day voiding diary • Change in the total number of voids per day as measured by the 3-day voiding diary • Change in 24-hour pad weight as measured by the 24-hour pad weight test • Change in the Bladder Stress Test (BST) (at Week 12 only) • Change in subject-reported impression of SUI severity as measured by the Patient Global Impression of Severity scale (PGI-S) • Change in subject-reported impression of SUI improvement as measured by the Patient Global Impression of Improvement scale (PGI-I) • Change in subject-reported urogenital distress as measured by the Urinary Distress Inventory questionnaire (UDI-6) • Change in subject-reported impact of urinary incontinence on daily life as measured by the Incontinence Impact Questionnaire (IIQ-7) Short Form • Change in subject-reported impact of urinary incontinence on daily life as measured by the Incontinence Quality of Life questionnaire (I-QOL) • Change in subject-reported sexual function as measured by the Female Sexual Function Index questionnaire (FSFI) • Change in subject-reported assessment of fecal incontinence as measured by the Vaizey Incontinence Severity Score • Change in subject-reported stress incontinence, urge incontinence, and mixed incontinence as measured by the Medical, Epidemiological, and Social Aspects of Aging (MESA) incontinence questionnaire (Week 12 only) 
Exploratory Objectives - Efficacy
 
The exploratory efficacy objectives of this study are to assess the durability of the effect of treatment at Week 16, Week 20, and Week 28 in relation to the following:

--	---

- Responder rate, where a responder is defined as having a $\geq 50\%$ reduction compared to baseline in the mean number of stress incontinence episodes per day as assessed by the 3-day voiding diary
- Number of stress incontinence episodes per day as measured by the 3-day voiding diary
- Total number of voids per day as measured by the 3-day voiding diary
- Change in 24-hour pad weight as measured by the 24-hour pad weight test
- Subject-reported impression of SUI severity as measured by the PGI-S
- Subject-reported impression of SUI improvement as measured by the PGI-I
- Subject-reported urogenital distress as measured by the UDI-6

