For binary secondary endpoints (responders), the treatment effect will be estimated using a logistic regression model with treatment as a covariate.

For continuous secondary endpoints, treatment effects will be estimated using a mixed model repeated measures analysis (MMRM). The MMRM model will specify an unstructured variance/covariance matrix and will include treatment group, visit, and baseline as covariates.

For ordinal endpoints, treatment effects will be estimated using a proportional odds model.

Further details on the analysis of secondary efficacy endpoints will be provided in the SAP.

Analysis of Exploratory Efficacy Endpoints

Durability of treatment effect will be examined in the DS for the exploratory efficacy endpoints. Additional sensitivity analyses of exploratory and secondary efficacy

	
endpoints may also be conducted as exploratory analyses, including sensitivity analyses with regard to missing data. Further details of the exploratory analyses will be provided in the SAP.
 
Safety Analyses
 
All safety parameters (including AEs, vital signs, laboratory evaluations, SHBG, testosterone, and endometrial stripe thickness) will be summarized using the SA set. No formal hypothesis testing will be performed.
 
All AEs will be coded using the latest version of Medical Dictionary for Regulatory Activities (MedDRA). All treatment-emergent AEs (TEAEs) will be summarized and presented in the listings by the number of subjects reporting an event, the percentage of subjects with that event, the number of events, and the grade, duration, and relationship to treatment. Percentages will be based on the number of subjects who received each treatment during the study.
 
Clinical laboratory safety tests will be performed, and normal ranges will be provided for each lab test. Values outside the normal range will be assessed for clinical significance by the investigator. Shift tables (change from baseline value to on-treatment values) will be presented for each laboratory measurement and assessment time. Each parameter outside the normal range will be designated as high (H) or low (L) in the individual data listings.

--	---

List of Abbreviations

Abbreviation	Definition
AE	adverse event
ALT	alanine aminotransferase
AST	aspartate aminotransferase
BST	bladder stress test
CFR	Code of Federal Regulations
DS	durability set
ECG	electrocardiogram
eCRF	electronic case report form
FAS	full analysis set

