6.1.2 Study Visit 1: Week 0, Clinic Visit

Concomitant medications and AEs will be reviewed. The results of the 24-hour pad weight test and the 3-day voiding diary will be reviewed, and continued eligibility for enrollment will be evaluated, also considering the results of laboratory tests during screening. A subject meeting the inclusion and exclusion criteria after all screening study measures have been completed and reviewed will be randomly assigned to treatment (randomization).

Vital signs will be obtained, a dipstick urinalysis will be performed, and the subject will complete the UDI-6, IIQ-7 Short Form, I-QOL, FSFI, PGI-S, and Vaizey Incontinence Severity questionnaires.

Study drug will be dispensed with administration instructions, and each package will be preprinted with a medication identification number. The medication identification number assigned to the subject will be noted in the eCRF for study drug. The subject will take the first dose of study drug during this visit.

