6.2.3 Patient Global Impression of Severity

The PGI-S is a global rating of subject-reported impression of SUI severity using a 4-point scale (Appendix 12.3). Validity of the PGI-S has been established for application in SUI.

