7.2 Secondary Efficacy Endpoints

The secondary efficacy endpoints in this study are the following assessments compared to baseline at each visit during the treatment period:

- Responder rate, where a responder is defined as having a $\geq 50\%$ reduction compared to baseline in the mean number of stress incontinence episodes per day as assessed by the 3-day voiding diary
- Change in the number of stress incontinence episodes per day as measured by the 3-day voiding diary
- Change in the total number of voids per day as measured by the 3-day voiding diary
- Change in the mean number of stress incontinence episodes per day as measured by the 3-day voiding diary
- Change in 24-hour pad weight as measured by the 24-hour pad weight test
- Change in the results of the Bladder Stress Test (BST)
- Change in subject-reported impression of SUI severity as measured by the PGI-S
- Change in subject-reported impression of SUI improvement as measured by the PGI-I
- Change in subject-reported urogenital distress as measured by the UDI-6
- Change in subject-reported impact of urinary incontinence on daily life as measured by the IIQ-7 Short Form

- Change in subject-reported impact of urinary incontinence on daily life as measured by the I-QOL
- Change in subject-reported sexual function as measured by the FSFI
- Change in subject-reported assessment of fecal incontinence as measured by the Vaizey Incontinence Severity Score.
- Change in subject-reported stress incontinence, urge incontinence, and mixed incontinence as measured by the MESA incontinence questionnaire (Week 12 only)

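### PGI-S has a Visit 1 rating, but the proportional odds analysis specifies no baseline term and the endpoint is worded as change on a 4-point scale; a baseline-adjusted analysis of the visit category would be more efficient and easier to interpret

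*Combined protocol and SAP*

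**What the plan says.** Section 7.7.2 and the matching synopsis paragraph assign a model to each type of secondary endpoint:

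- **Binary:** logistic regression, with treatment named as the covariate.
- **Continuous:** "The MMRM model will specify an unstructured variance/covariance matrix and will include treatment group, visit, and baseline as covariates" (synopsis wording; 7.7.2 has the same content).
- **Ordinal:** "For ordinal endpoints, treatment effects will be estimated using a proportional odds model". No covariate, response variable or handling of visits is given, and no list says which endpoints are ordinal.

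Both places then add: "Further details on the analysis of secondary efficacy endpoints will be provided in the SAP". The SAP is to be finalized before unblinding; the text available for review contains the protocol only.

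Section 7.2 gives the endpoint, relative to baseline at each treatment-period visit, as: "Change in subject-reported impression of SUI severity as measured by the PGI-S". The synopsis and Section 2.2 word it in the same way. Section 6.2.3 describes the instrument: "The PGI-S is a global rating of subject-reported impression of SUI severity using a 4-point scale". Appendix 12.3 labels the categories 1 Normal, 2 Mild, 3 Moderate and 4 Severe.

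A baseline rating exists. At Visit 1, Section 6.1.2 states that "the subject will complete the UDI-6, IIQ-7 Short Form, I-QOL, FSFI, PGI-S, and Vaizey Incontinence Severity questionnaires", and Table 12–1 agrees. PGI-I differs: Appendix 12.4 shows a 7-category comparison with the time before study medication, and Table 12–1 first schedules it at Week 4.

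**The concern.** Two things combine. First, baseline is named for the continuous endpoints but not for the ordinal ones, although the PGI-S baseline is collected and is probably the best available predictor of the later rating. Leaving it out costs precision and leaves the estimate exposed to chance imbalance in starting severity.

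Second, change is an awkward response on four ordered categories, because the starting category limits how far a woman can improve. A common odds ratio for change then depends partly on how severe the women were at entry. It does not tell the reader how many end the treatment period Normal or Mild.

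At stake is the sensitivity and readability of one of the trial's two global patient ratings.

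**Working it through.** **1. The plan's own power figure, for scale (Section 7.4).** Inputs: 40% versus 60% response, two-sided 5%, 80% power, 25% discontinuation, 1:1:1 allocation.

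n = [1.960·√(2·0.5·0.5) + 0.842·√(0.4·0.6 + 0.6·0.4)]² / 0.20² = (1.386 + 0.583)² / 0.04 ≈ 97 per arm.

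97 / 0.75 ≈ 130 per arm, or 390 in total, against the stated 400 or so. Conversely, 400/3 ≈ 133 per arm leaves about 100 completers, and power is 81.2%. The figure reproduces, but it concerns the primary responder endpoint. No power is claimed for PGI-S. It serves here only to justify 100 per arm below.

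**2. What change can and cannot show (Appendix 12.3 coding).** Change = visit score − Visit 1 score.

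| Visit 1 | Best possible change | End state at best |
|---|---|---|
| Normal (1) | 1 − 1 = 0 | Normal |
| Mild (2) | 1 − 2 = −1 | Normal |
| Moderate (3) | 1 − 3 = −2 | Normal |
| Severe (4) | 1 − 4 = −3 | Normal |

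Mild to Normal scores −1, the best result open to that woman. Severe to Mild scores −2, although she still has symptoms. Severe to Moderate also scores −1 and so ties with Mild to Normal. The same end state maps to different changes according to entry severity, so the odds ratio for change depends on the baseline mix.

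**3. Cost in power.** The documents give no PGI-S distribution, correlation or treatment effect, so all of these are assumed. Both simulations compare two arms of 100 with a Wald test at |z| > 1.96.

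*Simulation A:* 700 runs; latent normal scores cut into four categories; baseline Normal/Mild/Moderate/Severe 2/25/50/23%; latent treatment shift 0.4 SD; correlation on the latent scale; baseline entered as category.

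| Correlation | Change, no baseline | Visit category, no baseline | Visit category + baseline | Loss with change |
|---|---|---|---|---|
| 0.3 | 56.3% | 75.0% | 78.4% | 22.1 |
| 0.5 | 67.4% | 72.9% | 81.1% | 13.7 |
| 0.7 | 79.9% | 75.6% | 88.3% | 8.4 |

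*Simulation B:* 1,500 runs; proportional odds with conditional odds ratio 2.0; baseline 2/28/50/20%; placebo Week 12 distribution 10/35/37/18%; correlation between observed scores (rounded); baseline entered as a linear score.

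| Correlation | Change, no baseline | Visit category, no baseline | Visit category + baseline | Loss with change |
|---|---|---|---|---|
| 0 | 51.1% | 74.3% | 74.6% | 23.5 |
| 0.3 | 63.5% | 71.3% | 75.7% | 12.3* |
| 0.5 | 68.2% | 59.5% | 74.3% | 6.1 |
| 0.7 | 68.1% | 45.0% | 70.7% | 2.6 |

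*From unrounded values, 75.73 − 63.47.

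The Monte Carlo standard error of a single power figure is at most about 1.9 points in A (√(0.563·0.437/700)) and 1.3 points in B (√(0.511·0.489/1500)).

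**4. Validity.** With no treatment effect, simulation A at correlation 0.5 rejected in 5.3% of runs (change), 5.7% (visit category, no baseline) and 4.9% (visit category with baseline). In B the models without baseline rejected in 4.3% to 5.8%, and the visit category with baseline in 4.9% to 5.6%. All are nominal within simulation error.

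**5. Keeping change but adding baseline.** In B this gave 76.7%, 77.6%, 75.2% and 70.9% power at correlations 0, 0.3, 0.5 and 0.7, but rejected in 7.4% of null runs at correlation 0. The visit category with baseline has similar power and did not show that excess.

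**The case against.** The strongest reply is that the plan is silent here, and silence is not an error. The ordinal sentence names no covariates at all, not even treatment, and further detail is left to the SAP. A reader might infer that baseline has been excluded by design; the text does not say so. It supports only the statement that no baseline term is specified.

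A reader might also infer that raw change is the defined model response. That is the literal reading of the endpoint, but not a confirmed one. The same change wording is applied to PGI-I, which has no baseline rating, and the exploratory lists in Sections 2.3 and 7.3 name PGI-S without it. Nor does the protocol class PGI-S as ordinal. If it were treated as continuous, the mixed model with baseline would apply.

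Finally, a reader might conclude that the analysis ranks outcomes wrongly or gives a biased test. Steps improved and final category are different questions, and randomization keeps the test of either valid, as the null results show.

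These points stand and limit the wording of the concern. They do not remove it. Deferral explains the gap without filling it, and a literal reading leads to the less efficient analysis when the better one needs only data already collected.

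**Conclusion.** The point holds as a specification gap with a clear better choice. Read literally, the plan gives a valid but less efficient ordinal analysis of PGI-S change, whose odds ratio depends on the baseline mix.

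Against the baseline-adjusted visit category, the illustrative loss is about 3 to 22 points of power as the correlation falls from 0.7 to 0.3, and about 23 points at zero. Dropping the change score without adding baseline is not enough: the unadjusted category falls behind by 12.7 points (A, 88.3 − 75.6) and 25.7 points (B, 70.7 − 45.0) at 0.7.

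The sizes rest on assumed distributions and effects, and the two simulations measure correlation on different scales. In both, however, the visit category with baseline had more power than either unadjusted analysis at every correlation tried, so the choice does not require knowing the correlation.

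The consequence is limited. PGI-S is one of 14 secondary endpoints listed in Section 7.2 of a Phase 2 trial, and the primary responder analysis is unaffected.

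**What to change.** Before unblinding, in Section 7.7.2, the synopsis and the SAP:

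1. List the endpoints treated as ordinal.
2. For PGI-S, state that the response is the category at each visit (1 to 4), analysed by a proportional odds model with treatment group and Visit 1 PGI-S. Enter Visit 1 PGI-S as a linear score, or as categories with a sparse Normal level pooled. At the 2% assumed above, Normal would hold about 0.02 × 400 = 8 women in the whole trial.
3. Report the common odds ratio for each dose against placebo, labelled as conditional on baseline PGI-S.
4. Align the PGI-S endpoint wording in the synopsis, Section 2.2 and Section 7.2, so that it no longer describes a change score while the model uses the visit category.
5. State separately that PGI-I is analysed as the observed category because it has no baseline rating. Using Visit 1 PGI-S as a covariate for PGI-I is optional.

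The cost is a few sentences and consistent edits in several places, with no new data, visits or participants. The odds ratio will then describe end-of-period severity given baseline, not steps improved, and the report should say so. If the SAP already specifies this model, only the protocol wording needs aligning.

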1.1 Background and Rationale

Enobosarm (GTx-024) is an orally bioavailable and tissue-selective nonsteroidal selective androgen receptor modulator (SARM) that has demonstrated androgenic and anabolic activity and is currently being evaluated as a potential treatment for stress urinary incontinence (SUI) in postmenopausal women.

Urinary incontinence and pelvic floor disorders are major health problems for women, especially as they age (Luber 2004). Pelvic floor muscle relaxation has been found to correlate with lower urinary tract symptoms including SUI. Muscles of the pelvic floor and lower urinary tract are crucial for supporting the pelvic organs and micturition; however, damage to the muscles and/or lack of hormonal stimulation are thought to contribute to pelvic organ prolapse and urinary incontinence.

Although anabolic steroids may increase muscle mass and strength, lack of oral bioavailability and known potential risks have limited their use (Mohler et al 2009). Nonsteroidal SARMs have potential to achieve benefits of anabolic steroid therapy (improved muscle mass, cholesterol/triglyceride levels, glucose metabolism, and bone density) with fewer adverse effects, such as hirsutism and acne, in women.

Both nonclinical and clinical data suggest that SARMs may provide a new therapeutic option for pelvic floor and lower urinary tract disorders, as both testosterone and its more potent metabolite, dihydrotestosterone, have anabolic effects on muscle.

GTx-024 has demonstrated androgenic and anabolic activity in male and female rat models. GTx-024 has consistently been observed to increase body weight, specifically muscle, in female rats. In a male rat model with castrate levels of serum testosterone, GTx-024 has the ability to induce hypertrophy of the levator ani muscle to approximately 120% of a noncastrate male.

Another SARM (GSK2849466A), studied in an ovariectomized rat model that mimics SUI by disrupting urethral continence, was shown to increase urethral baseline pressure and the amplitude of urethral responses during sneezing by 64% and 74%, respectively, compared to the vehicle control (GTx, Inc. 2017; Kadekawa et al 2015). Furthermore, all of the rats (8/8) in the vehicle-treated group experienced fluid leakage during sneezing whereas only 1 of the

rats (1/8) in the SARM-treated group experienced such leakage upon similar challenge. Histologically, the SARM-treated animals had a reversal of the atrophy in urethral muscle observed in the control group. This preliminary in vivo study supports the clinical study of SARMS for the treatment of SUI.

A proof-of-concept study is currently ongoing to investigate the effect of GTx-024 on symptoms of SUI in postmenopausal women. Available data from the 18 subjects dosed at 3 mg GTx-024/day for 12 weeks showed a mean reduction in stress incontinence episodes of 81%, with all 18 subjects seeing a clinically significant reduction ($\geq 50\%$ reduction in stress leaks) in the number of stress incontinence episodes by Week 12.

2 Study Objectives

2.1 Primary Objective

The primary efficacy objective of this study is to compare the efficacy of GTx-024 (1 mg and 3 mg administered once daily) to that of placebo by evaluating the mean number of subject-reported stress incontinence episodes per day through a responder analysis, where a responder is defined as having a $\geq 50\%$ reduction at the end of treatment (Week 12) compared to baseline in the mean number of stress incontinence episodes per day as assessed by the 3-day voiding diary. Subjects who have missing diary data for the Week 12 visit will be counted as non-responders for this analysis.

2.2 Secondary Objectives

The secondary efficacy objectives in this study are to compare, at each visit during the treatment period, the efficacy compared to baseline of two doses of GTx-024 (1 mg and 3 mg administered once daily) to that of placebo in relation to the following:

- Responder rate, where a responder is defined as having a $\geq 50\%$ reduction compared to baseline in the mean number of stress incontinence episodes per day as assessed by the 3-day voiding diary
- Change in the number of stress incontinence episodes per day as measured by the 3-day voiding diary
- Change in the total number of voids per day as measured by the 3-day voiding diary
- Change in 24-hour pad weight as measured by the 24-hour pad weight test
- Change in the Bladder Stress Test (BST) (at Week 12 only)
- Change in subject-reported impression of SUI severity as measured by the Patient Global Impression of Severity scale (PGI-S)
- Change in subject-reported impression of SUI improvement as measured by the Patient Global Impression of Improvement scale (PGI-I)
- Change in subject-reported urogenital distress as measured by the Urinary Distress Inventory questionnaire (UDI-6)

- Change in subject-reported impact of urinary incontinence on daily life as measured by the Incontinence Impact Questionnaire (IIQ-7) Short Form
- Change in subject-reported impact of urinary incontinence on daily life as measured by the Incontinence Quality of Life questionnaire (I-QOL)
- Change in subject-reported sexual function as measured by the Female Sexual Function Index questionnaire (FSFI)
- Change in subject-reported assessment of fecal incontinence as measured by the Vaizey Incontinence Severity Score
- Change in subject-reported stress incontinence, urge incontinence, and mixed incontinence as measured by the Medical, Epidemiological, and Social Aspects of Aging (MESA) incontinence questionnaire (Week 12 only)

2.3 Exploratory Efficacy Objectives

The exploratory efficacy objectives of this study are to assess the durability of the effect of treatment at Week 16, Week 20, and Week 28 in the first 225 randomized subjects in relation to the following:

- Responder rate, where a responder is defined as having a $\geq 50\%$ reduction compared to baseline in the mean number of stress incontinence episodes per day as assessed by the 3-day voiding diary
- Number of stress incontinence episodes per day as measured by the 3-day voiding diary
- Total number of voids per day as measured by the 3-day voiding diary
- Change in 24-hour pad weight as measured by the 24-hour pad weight test
- Subject-reported impression of SUI severity as measured by the PGI-S
- Subject-reported impression of SUI improvement as measured by the PGI-I
- Subject-reported urogenital distress as measured by the UDI-6
- Subject-reported impact of urinary incontinence on daily life as measured by the IIQ-7 Short Form

- Subject-reported impact of urinary incontinence on daily life as measured by the I-QOL
- Subject-reported sexual function as measured by the FSFI
- Subject-reported assessment of fecal incontinence as measured by the Vaizey Incontinence Severity Score

Additional sensitivity analyses may be included in exploratory analyses.

